### **2.9.1.2 Palatability questionnaire**

The palatability questionnaire consists of 4 items. Two items measure the taste (item 1) and aftertaste (item 2) of the medication and are scored on a 5 point response scale with the response format 1 “Very good”, 2 ”Good”, 3 “Not good or bad” for PRO/ 3 “Neither good nor bad” for ObsRO, 4 “Bad” and 5 “Very bad”. The PRO aftertaste item offers an additional response option of “no aftertaste”. This response option will be recoded such that all patients have a response, for example, patients who choose this option will be coded 0 and patients who rated the aftertaste will be coded 1. This will result in binary (yes/no) aftertaste item.

Note for ObsRO: Item 1 the response format for 3 refers to “Neither good nor bad” and for Item 3 the response format 1 refers to “Swallowed and retained ALL of the medicine”. Same scoring rule will be used for both ObsRO and PRO.

The remaining palatability items refer to whether the medication was taken (i.e., swallowed or vomited) and how the patient perceived the amount of medication to be taken.

A summary of Items 1, 3 and 4 leading to the palatability summary score will be constructed using the following rules:

Recode Item 1              Very good, Good & Not good or bad =1

                            Bad & Very bad = 2

Recode Item 3              Swallowed ALL of the medicine =1

Spat out SOME of the medicine & Spat out ALL of the medicine and swallowed none =2

Vomited within 30 minutes after swallowing the medicine = 3

Recode Item 4      Not enough liquid & Too much liquid = 1  
                         Just enough liquid = 2

No missing data will be imputed when calculating the palatability summary score.

The Table 2-3 presents the Items 1, 3 and 4 scoring matrix leading to the palatability summary score:

**Table 2-3      Scoring Matrix**

Palatability Score	Item1 – taste	Item3 – what happened	Item4 – amount	Definition
0	Bad & Very bad; 2	Vomited < 30 min; 3	Not enough too much; 1	Worst palatability
1	Bad & Very bad; 2	Vomited < 30 min; 3	Just enough; 2	1
2	Bad & Very bad; 2	Spat some/ all out; 2	Not enough too much; 1	2
3	Bad & Very bad; 2	Spat some/ all out; 2	Just enough; 2	3
4	Bad & Very bad; 2	Swallowed all; 1	Just enough; 2	4
5	Bad & Very bad; 2	Swallowed all; 1	Not enough too much; 1	5
6	V. good, Good & Not good/bad; 1	Vomited < 30 min; 3	Not enough too much; 1	6
7	V. good, Good & Not good/bad; 1	Vomited < 30 min; 3	Just enough; 2	7
8	V. good, Good & Not good/bad; 1	Spat some/ all out; 2	Not enough too much; 1	8
9	V. good, Good & Not good/bad; 1	Spat some/ all out; 2	Just enough; 2	9
10	V. good, Good & Not good/bad; 1	Swallowed all; 1	Not enough too much; 1	10
11	V. good, Good & Not good/bad; 1	Swallowed all; 1	Just enough; 2	Best palatability

The palatability summary score will be summarized using descriptive statistics by treatment arm, type of questionnaire (ObsRO questionnaire versus PRO questionnaire) and week (weeks 2, 3, 25 and core EOT). Additionally, absolute change from week 2 to week 25 and core EOT will be summarized including 95% confidence intervals for mean.

Graphical representation of this 11 point response scale will be provided over weeks by treatment and type of questionnaire. The y-axis will be the mean and SD and the x-axis will be the week number.

In addition, all of the 4 Items from the palatability questionnaire will be summarized using descriptive statistics by treatment arm, type of questionnaire and week using frequency counts and percentages for the FAS-3.

The number of patient completing the palatability questionnaire and the number of missing assessments will be summarized by treatment arm, type of questionnaire and week for the FAS-3.

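### In the palatability scoring matrix, scores 4 and 5 run against the order of the other five pairs, and neither SAP that carries the table explains why

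*SAP*

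**What the plan says.** Protocol section 10.5.3 says that the palatability score comes from a scoring matrix and leaves the details to the SAP. Section 2.9.1.2 of the primary-analysis SAP is therefore the place where the score is defined. It recodes three items:

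- Taste (item 1): "Very good, Good & Not good or bad =1"; the two bad answers become 2.
- Intake (item 3): a fully swallowed dose becomes 1, any spitting out becomes 2, and vomiting soon after the dose becomes 3.
- Amount (item 4): the right amount is coded "Just enough liquid = 2", and both wrong-amount answers become 1.

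Table 2-3 then assigns one score to each of the 12 combinations. Score 0 is labelled the worst palatability and score 11 the best; the rows between carry only their own number. The same matrix serves the patient and the observer questionnaires.

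The intake entry "Swallowed all; 1" stands in four rows: scores 4, 5, 10 and 11. The rows at issue are the two with bad taste. There, score 4 goes with just enough, and score 5 goes with the amount entry "Not enough too much; 1".

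Table 2-3 in section 2.9.5.2 of the End of Core Phase SAP has the same two rows in the same order.

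**The concern.** Two respondents in this cell give the same taste and intake answers: both disliked the taste and both took the whole dose. The one who also found the amount right receives the lower palatability score. Everywhere else in the table, finding the amount right adds a point.

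Palatability is a named secondary objective. The score is summarised by arm, questionnaire type and week, and its change from week 2 to week 25 and to the end of the core phase is reported with 95% confidence intervals. A programmer who follows the table as printed will carry the inconsistency into the means and into the change scores, where it can reverse the sign of a respondent's change.

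**Working it through.** **Inputs.** The recoded items and the 12 rows come from section 2.9.1.2 and Table 2-3 of the primary-analysis SAP. For taste and intake the lower code is the better answer. For amount the higher code is the better one, as the labels at scores 0 and 11 show.

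**Step 1: pairs that differ only in amount.**

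| Taste | Intake | Not enough / too much | Just enough | Difference |
|---|---|---|---|---|
| Bad | Vomited | 0 | 1 | +1 |
| Bad | Spat out | 2 | 3 | +1 |
| Bad | Swallowed all | 5 | 4 | **-1** |
| Good or neutral | Vomited | 6 | 7 | +1 |
| Good or neutral | Spat out | 8 | 9 | +1 |
| Good or neutral | Swallowed all | 10 | 11 | +1 |

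All 12 combinations occur exactly once, so no row is missing or duplicated.

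**Step 2: the rule that the table implies.** The SAP states no formula. The layout ranks by taste, then intake, then amount:

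score = 6 × (2 - item 1) + 2 × (3 - item 3) + (item 4 - 1)

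This reproduces 10 of the 12 rows. For example, good taste, swallowed all, just enough gives 6 × 1 + 2 × 2 + 1 = 11. The two failures are:

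- bad taste, swallowed all, just enough: 6 × 0 + 2 × 2 + 1 = 5, but the table has 4;
- bad taste, swallowed all, not enough or too much: 6 × 0 + 2 × 2 + 0 = 4, but the table has 5.

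Swapping these two scores makes all 12 rows fit.

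**Step 3: effect on one respondent's change.** A move within the cell from too much to just enough scores 4 - 5 = -1 as printed and 5 - 4 = +1 after a swap. A move from spat out to swallowed all, with bad taste and just enough throughout, scores 4 - 3 = +1 as printed and 5 - 3 = +2 after a swap. A respondent who gives the same answers at both visits has a change of 0 either way.

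**Step 4: effect on an arm mean at one visit.** Let s be the share of the arm in the cell and j the share of those who answer just enough. The printed score is 1 too low for the fraction j and 1 too high for the fraction 1 - j, relative to the swapped order. So

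mean shift = s × [-j + (1 - j)] = -s × (2j - 1)

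The documents give neither s nor j. For assumed values:

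| s | j | Mean shift |
|---|---|---|
| 0.40 | 0.80 | -0.40 × 0.60 = -0.24 |
| 0.60 | 0.95 | -0.60 × 0.90 = -0.54 |
| 0.40 | 0.50 | 0 |
| 0.40 | 0.30 | -0.40 × (-0.40) = +0.16 |

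**The case against.** The strongest reply is that the order may be the instrument's own key. Only the end points of the scale have verbal labels, no nested rule is written down, and the patient questionnaires are described in SAP section 2.9.1 as already psychometrically validated. The SAP's document history records that the palatability scoring rule was clarified in version 4.0, and the order survived unchanged into the End of Core Phase SAP. This stands to the extent that the documents cannot tell a transcription slip from a deliberate key, so the source must be checked before anything is swapped. It does not remove the point: neither SAP cites a key or explains the exception.

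A second reply is that the score is only descriptive. That is correct. No between-arm test or estimate of palatability is planned, and all four items are also tabulated separately by arm and week for FAS-3, which lets a reader see the raw answers, though not jointly.

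A reader might also infer that the inconsistency penalises the DT arm, because children on DT would dislike the taste yet swallow the dose. The documents do not support this. Protocol section 2.1 reports taste complaints among adults on DT and links bad taste to poorer compliance. It does not predict that DT children will be in this cell, and spitting out or refusing the dose fits the argument at least as well.

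**Conclusion.** The inconsistency is real and is wrong as written unless a scoring source outside the documents supports it. It affects two of 12 rows, by one point each on a 0 to 11 score, and only respondents with bad taste who swallowed everything. Calling it a reversal is an inference from the table's own direction and from the five other pairs.

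Its effect on any arm mean is unknown. In the assumed cases above it runs from -0.54 to +0.16, and it is zero when half of the cell answers just enough. A difference between arms cannot be derived from the documents and should not be claimed. Neither co-primary endpoint uses this score.

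**What to change.** 1. Check the order of scores 4 and 5 against the questionnaire's scoring source.
2. Unless that source has the printed order, swap the two scores in Table 2-3 of both SAPs, so that bad taste, swallowed all, just enough scores 5 and its partner scores 4.
3. Confirm which order was programmed. If it was the printed one, rerun the derived score and correct the palatability summaries already reported.
4. If the source does have the printed order, cite it in both SAPs and add a sensitivity summary with the two scores swapped.

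The edit itself is two cells per table and one derived variable. The larger cost is in the reports. Table 1-1 of the final-CSR SAP lists the palatability results as already presented in the End of Core Phase report and not to be repeated, so a correction means amending or annotating existing output.

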### **2.9.1.3 Compliance diary**

The Compliance questionnaire consists of 2 items. Item 1 assessed whether the medication was taken (yes/no) and Item 2 is a record of the time when the medication was taken with a not applicable option for patients who did not take their ICT.

The daily compliance questionnaire diary records will also be used to calculate the rate of dose violations. For a given day, a dose violation is defined as a dose that is either missed completely or not taken in accordance with the timing instruction (no later than 12:00 pm). The dose violation rate is calculated as:

$$[\text{Number of dose violations} / \text{Drug exposure (days)}] * 100$$

Weekly average of dose violation rate will be calculated and summarized using descriptive statistics by treatment arm, type of questionnaire (ObsRO questionnaire versus PRO questionnaire) and week (weeks 1, 13, 25, 37 and core EOT). Additionally, absolute change from week 1 will be tabulated including 95% confidence intervals for mean. A graphical representation will be provided over all week periods by treatment arm and type of questionnaire. The y-axis will be the mean and SD and the x-axis will be the corresponding week period (see [Table 4-3](#) for week periods definition).

Due to the use of ePRO there will be no individual items missing. The weekly average rates will be calculated when there are at least four non missing daily responses. For a given week the denominator will be the number of non-missing days. No additional imputation will be carried out.

The number of patients completing the compliance diary and the number of expected and missing days will be summarized by each treatment arm and type of questionnaire for the FAS-3.

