	The dose of deferasirox DT or granules should be adjusted if necessary every 3 months based on the trends in serum ferritin and investigator's judgement. ICT naïve patients can adapt dose after 4 weeks. Dose adjustments need to be made in steps of 5 or 10 mg/kg/day for deferasirox DT and of 3.5 or 7 mg/kg/day for deferasirox granules and are to be tailored to the individual patient's response and the therapeutic goal of (reduction of iron burden). In patients not adequately controlled with deferasirox DT doses of 30 mg/kg/day, doses of up to 40 mg/kg/day may be considered. In patients not adequately controlled with deferasirox granules doses of 21 mg/kg/day, doses of up to 28 mg/kg/day may be considered. The starting dose and the dose adjustment considerations must take into account that the therapeutic goal is reduction of iron burden (as opposed to maintenance of iron burden). Doses above 40 mg/kg/day for deferasirox DT and above 28 mg for deferasirox granules are not allowed.

Dose modifications for deferasirox	
500 – 1000 ng/mL	Dose reductions in steps of 5 to 10 mg/kg/day for deferasirox DT and of 3.5 or 7 mg/kg/day for deferasirox granules is required to maintain serum ferritin levels within the target range.
< 500 ng/ml	Interruption of study treatment is required until serum ferritin rises above 500 ng/mL
Changes in urine protein/creatinine ratio	
For patients who develop proteinuria or a worsening of pre-existing proteinuria (assessed by a dipstick) at any visit, urine samples should be collected and assessed by the central laboratory. [Egypt: Local laboratory] In case of a single increase of the urinary protein/creatinine ratio the assessment should be repeated at the next visit.	
> 0.5 (mg/mg) in two consecutive second-void urine samples (a minimum of 48h apart), if all other causes of proteinuria have been excluded.	Deferasirox dose reduction by 50%  When resolution of UPCR (<0.5mg/mg) at the next study visit, dose can be resumed again at 100%  If increase in UPCR >0.5mg/mg recurs again within 2 months after initial increase, therapy needs to be reduced to 50% of the last dose. If increase in UPCR does not recur after 2 months at reduced dose (50%) , study medication can be returned to 100% of the last dose

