**Table 2-2 Deferasirox: Study drug exposure**

Overall duration of exposure (day):	$[(\text{date of last study treatment}) - (\text{date of first study treatment}) + 1]$
Drug exposure on dose X (days)	$[(\text{date of last study treatment on dose X}) - (\text{date of first study treatment on dose X}) + 1]$
Average dose (planned and actual, in mg/kg/day):	Mean dose over all days between first and last dose, including interruptions: sum of all (X dose * corresponding duration of exposure on dose X) / overall duration of exposure
Cumulative dose (planned and actual, in mg/kg):	Sum over daily doses of all days between first and last dose
Total patient-years (years):	Overall duration of exposure (days) / 365.25
Percentage of planned dose taken:	$100 \times [\text{Cumulative actual dose} / \text{Cumulative planned dose}]$

The actual dose in mg/kg/day will be obtained by dividing the actual total daily dose administered in the DAR eCRF page by the last available weight at the time of dose administration reported in the vital signs eCRF page.

Overall duration of exposure, average planned and actual daily dose, cumulative actual dose, total patient-years and percentage of planned dose taken will be summarized by treatment arm for the core phase and for the entire granule period.

The following variables will also be summarized by treatment arm and for each phase as appropriate as:

- Duration of exposure will be categorized in the core phase as: <4 weeks, 4 to <12 weeks, 12-<20 weeks, 20-<28 weeks, 28-<36 weeks, 36-<44 weeks,  $\geq 44$  weeks; and in the entire granule period as: <6 months, 6-<12 months, 12-<24 months, 24-<36 months, 36-<48 months,  $\geq 48$  months).
- Deferasirox DT average dose will be categorized as: <15, 15 to <25, 25 to <35 and  $\geq 35$  mg/kg/day
- Deferasirox granule average dose will be categorized as: <10.5, 10.5 to <17.5, 17.5 to <24.5 and  $\geq 24.5$  mg/kg/day

In addition, the number of patients who have dose reduction, increase or dose interruption, with corresponding reasons and the average length of dose interruptions will be summarized.

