Dose reduction will be considered if the actual dose is not equal to 0 (or not counted as interruption) and [the planned dose level is lower than the previous non-missing planned dose level Or the dose change is equal to 'yes' and the actual total daily dose administered (mg) is lower ( $> 15\%$ ) than the calculated dose amount based on the planned dose (mg)]. Any dose change to correct a dosing error will not be considered a dose reduction (patient goes back to the previous planned/actual dose after a dose change due to dosing error). Number of reductions will be derived programmatically.

Dose increase will be considered if the actual dose is not equal to 0 (or not counted as interruption) and [the planned dose level is higher than the previous non-missing planned dose level Or the dose change is equal to 'yes' and the actual total daily dose administered (mg) is higher (> 15%) than the calculated dose amount based on the planned dose (mg)]. Note that a dose rechallenge i.e when a patient goes back to the previous planned dose after an interruption or a dose reduction is not considered as an increase.

Dose interruption will be considered if an actual dose of zero in a unit of time between two non-zero actual dosing records. Any rest period as part of the schedule is not considered as an interruption. For the purpose of summarizing interruptions and reasons, in case multiple entries for interruption that are entered on consecutive days with different reasons will be counted as separate interruptions. However, if the reason is the same in this mentioned multiple entries on consecutive days, then it will be counted as one interruption.

Furthermore, box plot of average actual daily dose will be plotted by month and treatment (see [Table 4-1](#) for month definition) on the core phase only.

For each patient, listings of each dose of the study drug administered along with dose change reasons will be produced.

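### The diary violation rate has no rule for ordered treatment holds: read literally, an answered 'no' on a hold day is a violation and stays in the denominator

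*SAP*

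**What the plan says.** **Numerator.** SAP Amendment 3 section 2.9.1.3 describes the diary as two items: "Item 1 assessed whether the medication was taken (yes/no) and Item 2 is a record of the time when the medication was taken"; the time item also offers a not-applicable answer. On any day, "a dose violation is defined as a dose that is either missed completely or not taken in accordance with the timing instruction". The section does not mention interruptions. End of Core SAP section 2.9.5.3 carries the same text.

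**Denominator.** Two appear in the same section. The displayed formula divides by drug exposure in days, a term the section does not define. For the weekly rates, "For a given week the denominator will be the number of non-missing days", and "The weekly average rates will be calculated when there are at least four non missing daily responses". The weekly rate is the one tabulated (weeks 1, 13, 25, 37 and core end of treatment) and plotted.

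**Exposure.** SAP Table 2-2 computes overall duration as last date minus first date plus 1, and describes the average dose as "Mean dose over all days between first and last dose, including interruptions". Section 2.6 identifies holds from the DAR: "Dose interruption will be considered if an actual dose of zero in a unit of time between two non-zero actual dosing records". Interruptions are summarised there with reasons and average length, but are not linked to the diary.

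**Holds.** Protocol Table 6-2 requires interruption or omission of doses in several situations. For ferritin below 500 ng/mL: "Interruption of study treatment is required until serum ferritin rises above 500 ng/mL". Protocol section 7.2.3 has the diary completed daily, with alarms, from Visit 3 to Visit 777, and states no pause during a hold.

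**The concern.** The endpoint in Protocol Table 3-1 and section 10.5.5 is deviation from dosing instructions. On a day of ordered interruption the instruction is to take nothing, so a child who takes nothing has followed it. The diary cannot show this: it has no field for an ordered hold, and the SAP expects no individual item to be missing, so 'no' with time not applicable is a complete entry. A program written from the text would score it as a missed dose.

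If a programmer instead decided that no dose was due and dropped the day from the numerator only, it would still sit among the non-missing days and pull the rate down. So the stated rule gives a wrong rate on either choice; this is more than a missing detail.

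What is at stake is the diary's value as a second view of adherence. Protocol section 2.2 calls for several measures because pill counts overestimate adherence. A diary rate that mixes ordered holds with missed doses is a weaker cross-check.

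**Working it through.** The plan states no figure for the diary rate, so there is none to reproduce. The SAP rule is applied to simple cases.

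**Inputs**
- T = 336 days: 48 weeks of core treatment (Protocol section 6.1.2) × 7.
- H = length of an ordered hold: 7, 14 or 28 days (assumption).
- v = true violation rate on days when a dose was due: 0%, 5% or 10% (assumption).
- The diary is answered on every day (assumption).

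**Formulas for one patient's rate over T**
- Literal: [v(T − H) + H] / T
- Hold days dropped from the numerator only: v(T − H) / T
- Hold days dropped from both: v(T − H) / (T − H) = v
- Excess of the literal rate over v: H(1 − v) / T

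**Results, T = 336**

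| H | v | Literal | Numerator only | Both | Literal excess |
|---|---|---|---|---|---|
| 7 | 10% | (32.9 + 7)/336 = 11.9% | 9.8% | 10% | 6.3/336 = 1.9 points |
| 14 | 5% | (16.1 + 14)/336 = 9.0% | 4.8% | 5% | 13.3/336 = 4.0 points |
| 28 | 10% | (30.8 + 28)/336 = 17.5% | 9.2% | 10% | 25.2/336 = 7.5 points |
| 28 | 0% | 28/336 = 8.3% | 0% | 0% | 8.3 points |

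Across holds of 7 to 28 days and true rates of 10% to 0%, the excess runs from 1.9 to 8.3 points. The 8.3 applies only to a patient with no other violations.

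**One week, no other violations**

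| Hold days | All answered 'no' | All left blank |
|---|---|---|
| 1 | 1/7 = 14.3% | 6 responses, rate 0% |
| 3 | 3/7 = 42.9% | 4 responses, rate 0% |
| 4 | 4/7 = 57.1% | 3 responses, no rate |
| 7 | 7/7 = 100% | no responses, no rate |

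The same fully held week is 100% or absent, depending only on whether the family kept answering the prompt.

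**Arm level.** If a share h of answered days is on hold, the literal rate is v + h(1 − v). With v equal in both arms, the literal difference between arms is (h₁ − h₂)(1 − v), which is zero when the hold shares are equal. The documents give neither share.

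**The case against.** The strongest reply is that the SAP is silent on holds. A missed dose can be read as presupposing a dose that was due, and a patient who holds as told has not deviated from instructions. That is a fair reading of the numerator. It does not rescue the weekly denominator, which is defined by non-missing entries and so keeps answered hold days.

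A reader might infer more than the documents support:

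- **That the SAP states that holds are violations.** It does not. This is the result of following the text literally.
- **That every hold day is counted.** Unanswered hold days drop out of the weekly rate, and a week with fewer than four entries has none.
- **That the overall denominator certainly includes holds.** Drug exposure in days is undefined in the section. Overall duration in Table 2-2 is the nearest definition and spans interruptions; the wording about including interruptions belongs to the average-dose row.
- **That a 28-day hold distorts the published table throughout.** For a patient who completes the core phase, it can touch at most one tabulated week.
- **That the arm comparison is biased.** Holds depend on toxicity and ferritin response, which might differ by formulation, but both arms are randomised under the same Table 6-2 criteria and nothing in the documents shows unequal hold time. Interruptions are summarised by arm, so a gross imbalance would be visible.

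These points limit the size and certainty of the effect; they do not supply the missing rule.

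**Conclusion.** The point stands as a defect in the derivation of a secondary endpoint. The rule has no exclusion for ordered interruptions, uses a diary that cannot identify them, and gives two denominators, one undefined. Taken literally, an answered hold day is a violation, and a fully held and answered week reads 100%.

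The size at patient level is about 1.9 to 8.3 points over 336 days, given holds of 7 to 28 days, true rates of 10% to 0%, and complete diaries. All three are assumptions, since the documents report neither hold frequency nor diary completion during holds. An effect on the difference between arms requires unequal hold time, or unequal diary completion during holds, and is not shown.

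The analysis is descriptive. The co-primary compliance endpoint is derived separately from stick pack and tablet counts, so alpha, power and sample size are unaffected. The correction is worth making because it is cheap and the current rate does not measure what the protocol names.

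**What to change.** In SAP Amendment 3 section 2.9.1.3 and End of Core SAP section 2.9.5.3:

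1. Use one denominator for all diary rates: days with a non-missing entry that do not fall in an ordered interruption. Replace drug exposure in days with this count.
2. Define an ordered interruption as a DAR-recorded interruption whose recorded reason shows that the investigator or the protocol required it. Key it on a zero actual dose, as SAP section 2.6 does; the SAP does not say that the planned dose is set to zero during a hold.
3. Remove the same days from the numerator. Omissions that the patient or caregiver initiated remain violations.
4. Apply the minimum of four responses to the days that remain.
5. Show by arm the number of diary days removed and the number that could not be classified.

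The final SAP records the diary results as already presented in the End of Core report and does not plan to repeat them. The corrected rate should therefore be a re-derived supplementary table beside the reported one.

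The cost is SAP wording and a day-level merge of diary and DAR; no new data are needed, because the DAR collects actual dose, reason for change and dates (Protocol section 6.5.3.2). There will be fewer evaluable weeks. Days with incomplete DAR dates cannot be classified, since the SAP imputes only the date of last dose. The documents do not list the DAR reason categories, so whether they separate ordered from self-initiated holds must be confirmed first.
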